21.2 Analysis Populations

- The Modified Intent-to-Treat (mITT) Population will include all randomized subjects who receive at least 1 dose of study drug and who contribute any postbaseline efficacy data to the study.
- The Per-Protocol Population will include the subset of the mITT population who complete the study as per protocol, have no missing primary endpoint data, and do not have any major protocol deviations.
- The Safety Population will include all subjects who receive 1 or more doses of study drug.

The safety analyses will be performed using the safety populations. The efficacy and pharmacodynamic analyses will be performed using the mITT and Per Protocol populations; analyses performed on the mITT population will be considered primary.

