11.4 Approximate Duration of Subject Participation

Subjects will participate in the study for a total of up to approximately 32 weeks, including a screening period of up to 28 days, an active treatment period of 24 weeks, and a follow-up visit 28 (\pm 5) days after the last dose of study drug.

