21.3 Efficacy Endpoints

21.3.1 Primary Efficacy Endpoint

The primary efficacy endpoint will be proportion of responders as assessed by SRI at Week 16.

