21.6 Efficacy Analysis

Subjects will be included in the efficacy analyses based on their treatment assignment. The primary endpoint is the proportion of SRI responders at Week 16. The proportions of SRI responders for the 2 treatment groups will be summarized descriptively by visit and treatment group in tabular format and compared using a 2-sided Pearson's chi-square test at a significance level of 0.05. If the responder or nonresponder count falls to equal or below 5 in either treatment group, 2-sided Fisher's exact test will be used instead. All quantitative secondary and exploratory endpoints will be analyzed using analysis of covariance models with treatment group as a factor and the baseline value of the corresponding endpoint as a covariate. Mixed model with repeated measurement will be performed as deemed necessary. Secondary and exploratory endpoints that are proportions will be analyzed using Pearson's chi-square test or Fisher's exact tests.

For the primary efficacy endpoint, subjects who do not provide data to allow classification as responders will be considered nonresponders, that is, missing data will be imputed as non-responder. A similar approach will be applied to secondary efficacy endpoints that are proportions; missing will be classified as not satisfying the conditions described for that endpoint. A full description of missing data imputation method for all endpoints will be described in the statistical analysis plan.

██
██
██
██
██
██

All subjects who receive at least 1 dose of study drug will be included in the safety analyses.

Adverse events will be coded using MedDRA (version 19.0 or higher) by preferred term within system organ class. The number of AEs and the number of subjects reporting AEs will be listed and summarized descriptively by body system, preferred term, severity, and causality for each treatment group. Only TEAEs (events that are new in onset or aggravated in severity following treatment) will be included in all summaries. SAEs (including death) will be summarized.

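### The primary mITT set drops dosed subjects with no post-baseline efficacy data, so nonresponder imputation never reaches them, and Per-Protocol requires completing a study that runs past the Week 16 endpoint

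*Combined protocol and SAP*

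**What the plan says.** Section 21.2 (Analysis Populations) defines mITT as randomized subjects "who receive at least 1 dose of study drug and who contribute any postbaseline efficacy data to the study", and states that "analyses performed on the mITT population will be considered primary". The Per-Protocol set is the part of mITT "who complete the study as per protocol, have no missing primary endpoint data, and do not have any major protocol deviations". Efficacy is analysed in these two sets only. The Safety Population, which needs one dose and nothing more, is used for safety alone.

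Section 21.3.1 fixes the endpoint: "The primary efficacy endpoint will be proportion of responders as assessed by SRI at Week 16". Section 21.6 gives the missing-data rule: "subjects who do not provide data to allow classification as responders will be considered nonresponders, that is, missing data will be imputed as non-responder". It leaves the full account of imputation to a statistical analysis plan, and the document provided contains no separate text of one.

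Section 11.4 sets "an active treatment period of 24 weeks, and a follow-up visit 28" (± 5) days after the last dose, so completion lies well beyond Week 16. Section 21.11 allows for 2 of 162 randomized subjects failing to qualify for mITT. It does not say in which arm, or whether they would lack a dose or lack data.

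**The concern.** The two rules together treat nearly identical dropouts in opposite ways. By Table 8-1, SLEDAI-2K is the only SRI component repeated at Week 2. A dosed subject who provides that one score and then disappears is in mITT and counts as a nonresponder. A dosed subject who disappears a few days earlier has even less data, yet is removed from the analysis. Whether data exist is settled after randomization and can depend on treatment, for example through an adverse reaction to early doses. If such losses were concentrated in one arm, that arm's response rate would rise because its failures had left the denominator. Per-Protocol is a subset of mITT, so neither planned efficacy set would reveal this.

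The Per-Protocol definition has a different fault. A subject with a complete, compliant Week 16 SRI is deleted if he or she leaves between Week 16 and the end of follow-up. Section 12.1 encourages corticosteroid taper between Weeks 16 and 24, and Section 23.1 allows withdrawal for lack of efficacy. Neither event makes the Week 16 result less compliant with the protocol.

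**Working it through.** **1. The plan's own figure.** Inputs from Sections 21.6 and 21.11: 80 per arm, 30% vs 55%, two-sided Pearson chi-square at 0.05. With the pooled variance under the null,

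power = Φ{[d − 1.96·√(2p̄(1−p̄)/n)] / √([p₁(1−p₁)+p₂(1−p₂)]/n)}.

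Here d = 0.25 and p̄ = 0.425. The null standard error is √(0.48875/80) = 0.0782 and the alternative one is √(0.4575/80) = 0.0756. So (0.25 − 0.1532)/0.0756 = 1.280 and power = 89.97%. The stated 90% reproduces (89.4% by exact enumeration), so the sample size is not in error.

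**2. Can two exclusions matter?** The response counts are illustrative; the number 2 comes from Section 21.11. The test is z = (p₂−p₁)/√[p̄(1−p̄)(1/n₁+1/n₂)], placebo listed first.

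| Case | Counts | z | p |
|---|---|---|---|
| All 162 counted | 24/81 vs 36/81 | 0.1481/0.0759 = 1.952 | 0.051 |
| One excluded per arm | 24/80 vs 36/80 | 0.1500/0.0765 = 1.960 | 0.05004 |
| Both excluded from Acthar | 24/81 vs 36/79 | 0.1594/0.0766 = 2.082 | 0.037 |

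The balanced split does not cross 0.05; the one-sided split does. The window is narrow. With 35 Acthar responders, two Acthar exclusions move p from 0.073 to 0.054. With 37, p moves from 0.035 to 0.025. Neither changes the conclusion. Near the planned effect (24/81 vs 44/81) p is about 0.0015 before any exclusion.

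**3. Type I error of the mITT test.** Take as the null that response rates over all 81 per arm, with the excluded counted as nonresponders, are both 30%. An arm that loses k subjects then shows 0.30 × 81/(81−k) in mITT. Exact enumeration gives the following; 4 and 8 are assumed counts.

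| Exclusions, all from Acthar | Acthar rate in mITT | Rejection rate |
|---|---|---|
| 0 | 30.0% | 5.0% |
| 2 | 30.8% | 5.2% |
| 4 | 31.6% | 5.4% |
| 8 | 33.3% | 7.8% |

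With equal exclusions in both arms (4 and 4, or 8 and 8) it stays at 5.0%.

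**4. Power after the fix.** Assume 30% and 55% among subjects with data, with the 2 excluded subjects returned as nonresponders among 81 per arm. The formula of step 1 with n = 81 gives:

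| Returned, placebo/Acthar | Rates over 81 | Power |
|---|---|---|
| 1/1 | 0.30×80/81 = 29.6%; 0.55×80/81 = 54.3% | 89.7% |
| 0/2 | 30.0%; 0.55×79/81 = 53.6% | 86.9% |
| 2/0 | 0.30×79/81 = 29.3%; 55.0% | 92.0% |

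**5. Per-Protocol.** Suppose a fraction d of Week 16 nonresponders, and no responders, leave after Week 16. The observed rate is p/[p+(1−p)(1−d)]. The values of d are assumed.

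- d = 20% placebo, 10% Acthar: 30% becomes 0.30/0.86 = 34.9% and 55% becomes 0.55/0.955 = 57.6%. The difference falls from 25 to 22.7 points. A common rate of 40% becomes 0.40/0.88 = 45.5% vs 0.40/0.94 = 42.6%, against Acthar.
- With the two values of d exchanged: 0.30/0.93 = 32.3% vs 0.55/0.91 = 60.4%. The difference rises to about 28.2 points, in favour of Acthar.

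The sign depends on which arm loses more nonresponders, and the documents give no basis for predicting that.

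**The case against.** The strongest reply is that Section 21.2 says who is analysed and Section 21.6 says how missing values are handled among them. Applied together they give one workable rule: impute within mITT. That is correct. A reader might infer that the two sections contradict each other, or that the sets are chosen on the SRI result; the text supports neither. Selection is on dosing, data availability, completion and deviations.

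Second, the Early Termination visit closes most of the gap. Section 23.1 requires it of all who terminate early, and the list in Section 15.7 includes SLEDAI-2K, BILAG-2004 and PGA. Section 23.1 calls these safety assessments, but the efficacy items are on the list. A subject who stops in the first fortnight and attends is therefore in mITT, and with no Week 16 SRI counts as a nonresponder. Only very early leavers who also miss that visit are lost. This stands, and it is why the expected effect is small.

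Third, a flip across 0.05 needs a borderline result and a one-sided split. A reader might infer that the primary conclusion is in real danger. Nothing in the documents points to unequal losses before Week 2, and Section 10.4 reports the pilot doses as well tolerated.

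Fourth, Per-Protocol is supportive and cannot change the primary test. This also stands. To infer that the set favours Acthar, or is worthless as a check, goes further than the documents allow.

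What survives is that the boundary in mITT has no stated rationale and no planned analysis shows its effect. A later account of imputation would not restore subjects whom the population definition leaves out.

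**Conclusion.** The point holds as a should-fix, a cheap improvement. As written, the nonresponder rule stops short of dosed subjects with no post-baseline efficacy data, and no broader efficacy set is defined as a backstop. At the 2 exclusions the plan expects, the effect is negligible if they are balanced. If both fall in the Acthar arm, type I error is about 5.2%, and only a result already close to 0.05 could change sides. Reaching 7.8% takes 8 exclusions, all in one arm, which the documents do not suggest. The Per-Protocol definition can bias the supportive comparison in either direction.

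These sizes rest on assumed response counts, arm splits and post-Week 16 withdrawal rates; only the total of 2, the arm sizes and the 30% and 55% rates are the plan's. If the 2 expected subjects are never dosed, rather than dosed without data, deleting the post-baseline clause does not change their status.

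**What to change.** In Section 21.2, define the primary efficacy population as all randomized subjects who receive at least one dose, analysed as randomized, and delete the post-baseline-data condition. State in Section 21.6 that a missing Week 16 SRI is nonresponse for every member of that set. Define Per-Protocol by Week 16 status: Week 16 SRI available and no major deviation up to and including that visit, with no requirement to complete Week 24 or follow-up.

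Restate Section 21.11 with up to 81 per arm analysed, giving power of 89.7% for one returned nonresponder per arm and the range of 86.9% to 92.0% by arm split.

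The cost is wording only: the Safety Population already identifies the dosed subjects, and no new data are needed. The downside is slightly lower response rates and possibly slightly lower power. The change should be made before unblinding, since a later change of denominator would look data-driven.

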21.3 Efficacy Endpoints

21.3.1 Primary Efficacy Endpoint

The primary efficacy endpoint will be proportion of responders as assessed by SRI at Week 16.

21.3.2 Secondary Efficacy Endpoints

- Change from baseline over time in SLEDAI-2K (Week 0 to 16).
- Time to first response as assessed by SRI.
- Change from baseline over time in total BILAG-2004 (Week 0 to 16).
- Change from baseline over time in PGA (Week 0 to 16).
- Proportion of subjects with decrease from baseline of ≥ 4 points in SLEDAI-2K over time (Week 0 to 16).
- Change from baseline in CLASI-Activity score over time (Week 0 to 16) in subjects with CLASI-Activity at baseline.
- Change from baseline (Week 0 to 16) in 28 Joint Count (tender and swollen) in subjects with tender and swollen joints at baseline.

21.3.3 Exploratory Endpoints

-
- | Row | Bar Length (approx. % of total width) |
|-----|---------------------------------------|
| 1 | 85 |
| 2 | 95 |
| 3 | 100 |
| 4 | 10 |
| 5 | 95 |
| 6 | 90 |
| 7 | 10 |
| 8 | 65 |
| 9 | 75 |
| 10 | 100 |
| 11 | 25 |
| 12 | 100 |
| 13 | 95 |
| 14 | 20 |
| 15 | 75 |
| 16 | 65 |

21.4 Safety Endpoints

- Summary of general safety profile, including adverse events (serious and non-serious), vital signs and laboratory assessments by study period and over the entire study.

21.5 Subject Characteristics

21.5.1 Demographics

The demographic information will be summarized for each analysis population by treatment group.

21.5.2 Medical and Surgical History

Prior medical conditions or procedures will be summarized by body system and treatment group.

21.5.3 Prior and Concomitant Medications

Prior and concomitant medications will be coded according to the WHO Drug Dictionary. The incidence (number and percent) of prior and concomitant medication use will be summarized by treatment group.

21.5.4 Subject Disposition and Exposure to Study Drug

Subject disposition will be summarized. The number of subjects who complete the study and who do not complete the study along with the reasons for discontinuation from the study will be summarized.

21.6 Efficacy Analysis

Subjects will be included in the efficacy analyses based on their treatment assignment. The primary endpoint is the proportion of SRI responders at Week 16. The proportions of SRI responders for the 2 treatment groups will be summarized descriptively by visit and treatment group in tabular format and compared using a 2-sided Pearson's chi-square test at a significance level of 0.05. If the responder or nonresponder count falls to equal or below 5 in either treatment group, 2-sided Fisher's exact test will be used instead. All quantitative secondary and exploratory endpoints will be analyzed using analysis of covariance models with treatment group as a factor and the baseline value of the corresponding endpoint as a covariate. Mixed model with repeated measurement will be performed as deemed necessary. Secondary and exploratory endpoints that are proportions will be analyzed using Pearson's chi-square test or Fisher's exact tests.

For the primary efficacy endpoint, subjects who do not provide data to allow classification as responders will be considered nonresponders, that is, missing data will be imputed as non-responder. A similar approach will be applied to secondary efficacy endpoints that are proportions; missing will be classified as not satisfying the conditions described for that endpoint. A full description of missing data imputation method for all endpoints will be described in the statistical analysis plan.

██
██
██
██
██
██

All subjects who receive at least 1 dose of study drug will be included in the safety analyses.

Adverse events will be coded using MedDRA (version 19.0 or higher) by preferred term within system organ class. The number of AEs and the number of subjects reporting AEs will be listed and summarized descriptively by body system, preferred term, severity, and causality for each treatment group. Only TEAEs (events that are new in onset or aggravated in severity following treatment) will be included in all summaries. SAEs (including death) will be summarized.

Clinical laboratory tests (hematology, lipid panel, blood chemistry, and urinalysis); [REDACTED] and C3, C4, and anti-ds DNA antibodies results will be listed by subject and summarized by visit and treatment group. Categorical laboratory results will be presented with the frequency and percentage in each category by treatment group. Change from baseline at each visit will also be summarized. Shift tables will be generated if applicable. Select laboratory parameters may be presented graphically. Abnormal laboratory values will be identified and analyzed.

Vital sign results (heart rate, diastolic/systolic blood pressures, respiratory rate, and body temperature) and corresponding changes from baseline values will be summarized at each visit with descriptive statistics by treatment group.

Hospital admissions and the reason for each admission will be listed and summarized descriptively by visit and treatment. The cumulative number of hospital admissions will be compared between treatment groups at Week 24 with a 2-sided Pearson's chi-square test or Fisher's exact test at a significance level of 0.05.

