12 STUDY DESIGN

12.1 Description

This is a randomized, placebo controlled, double blind study. Following a screening period of up to 28 days, subjects with persistently active SLE and moderate to severe rash and/or arthritis despite receiving corticosteroids (7.5 mg to 30 mg per day of prednisone or equivalent) for \geq 4 weeks prior to screening, will be randomized in a 1:1 ratio to receive 1 mL (80 U) of Acthar or

matching placebo. At randomization, subjects will be stratified by prednisone equivalent dose (≤ 20 mg/day vs > 20 mg/day). During Weeks 1 to 4, 1 mL (80 U) of Acthar or volume matched placebo will be administered SC every other day. For the remainder of the study (Weeks 5 to 24), Acthar 1 mL (80 U) or volume matched placebo will be administered SC 2x/week. The primary efficacy endpoint is the SRI at Week 16. Corticosteroid taper may be attempted and is encouraged between Weeks 16 and 24 if medically appropriate; the taper rate and schedule will be at the discretion of the individual investigator. All subjects will have a follow-up visit 28 (± 5) days after the last dose of study drug.

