16.1 Methods of Assigning Subjects to Treatment Groups

16.1.1 Randomization and Stratification

Subjects will be randomized according to computer-generated allocation scheme to receive either Acthar 1 mL (80 U) or placebo 1 mL administered every other day for 4 weeks followed by 2x/week for 20 weeks. The randomization will be stratified by location (US or outside the US) and prednisone equivalent dose (≤ 20 and > 20 mg/day). For each stratum, a separate randomization scheme will be produced. Both investigators and the subjects will be blinded to the treatment assignment. A block randomization will be performed. The biostatistician will decide on the details at the time of the creation of the randomization scheme.

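### Randomisation is stratified by location and prednisone dose but the planned tests ignore the strata: a conservative mismatch that gives up a little power and costs only wording to repair

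*Combined protocol and SAP*

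**What the plan says.** All references are to the combined protocol and SAP.

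- **Section 16.1.1 (Randomization and Stratification):** "The randomization will be stratified by location (US or outside the US) and prednisone equivalent dose", with the dose cut at 20 mg/day. It continues "For each stratum, a separate randomization scheme will be produced" and "A block randomization will be performed". Two binary factors give four strata. Block size is left to the biostatistician.
- **Section 12.1 (Description):** "At randomization, subjects will be stratified by prednisone equivalent dose". Location is not mentioned.
- **Section 21.6 (Efficacy Analysis), primary endpoint:** the response proportions are "compared using a 2-sided Pearson's chi-square test at a significance level of 0.05", with Fisher's exact test as the small-count fallback. Neither uses strata.
- **Section 21.6, other endpoints:** proportions get Pearson or Fisher. Quantitative endpoints get "analysis of covariance models with treatment group as a factor and the baseline value of the corresponding endpoint as a covariate". A mixed model is left optional and its terms are not listed.
- **Section 21.11:** 80 analysed per arm, 30% against 55%, 90% power at the 0.05 level.

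No readable section puts either stratification factor into an analysis.

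**The concern.** Blocking within strata forces the arms to be nearly balanced on location and steroid dose. Differences in response between strata therefore contribute almost nothing to the sampling variation of the treatment difference. Pearson's variance is built from the overall response rate and still contains that between-stratum component. If either factor predicts response, the standard error used is larger than the true one. The test then rejects less often than 5% under the null, and some of the precision that the stratification bought is not used. The same applies to an ANCOVA with only treatment and baseline.

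The stake is efficiency and clean prespecification. With about 60 sites globally (Section 12.3), location could plausibly matter. If a stratified analysis is added only after unblinding, and the two p-values fall on opposite sides of 0.05, there is no agreed answer. A stratified analysis also cannot be programmed unambiguously while Sections 12.1 and 16.1.1 list different factors.

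**Working it through.** **1. Reproduce the plan's power.** Inputs from Section 21.11: n = 80 per arm, rates 0.30 and 0.55, mean 0.425, two-sided 0.05.

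- Null SE = √(2 × 0.425 × 0.575 / 80) = 0.0782.
- Alternative SE = √((0.30 × 0.70 + 0.55 × 0.45) / 80) = 0.0756.
- z = (0.25 − 1.96 × 0.0782) / 0.0756 = 1.28, so power = Φ(1.28) = 89.97%.

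The stated 90% reproduces. Exact enumeration of the uncorrected Pearson test gives 89.4%.

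**2. Size of the conservatism, by formula.** Let stratum s have share w and null response rate p, with overall rate p̄. Pearson uses a variance proportional to p̄(1 − p̄). Under stratified blocks the true variance is proportional to p̄(1 − p̄) − B, where B = Σ w(p − p̄)². With k = √(1 − B / [p̄(1 − p̄)]), the true type I error is about 2Φ(−1.96/k).

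The documents give no stratum shares or effects. Assume shares of 0.4, 0.1, 0.4, 0.1 (half the subjects in each location, 20% above 20 mg/day).

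- *Odds ratio 2 for each factor.* Rates 20, 34, 34, 50%; p̄ = 0.30. B = 0.4(0.10)² + 0.1(0.04)² + 0.4(0.04)² + 0.1(0.20)² = 0.0088. B/0.21 = 4.2%, k = 0.979, type I error about 4.5%.
- *Odds ratio 5 for location, 3 for dose.* Rates 12, 28, 40, 66%; p̄ = 0.302. B = 0.4(0.182)² + 0.1(0.022)² + 0.4(0.098)² + 0.1(0.358)² = 0.0300. B/0.2108 = 14.2%, k = 0.926, type I error about 3.4%.

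**3. Simulation.** 160 subjects, the same shares, permuted blocks of 4, common treatment odds ratio, 200,000 trials per cell. Overall rates are held at 30%/30% for type I error and 30%/55% for power.

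| Odds ratio, location / dose | Type I error, Pearson | Type I error, CMH | Power, Pearson | Power, CMH | Gain (points) |
|---|---|---|---|---|---|
| 1 / 1 | 5.1% | 5.0% | 89.6% | 89.6% | 0.0 |
| 1.5 / 1.5 | 4.9% | 5.0% | 89.9% | 90.2% | 0.3 |
| 2 / 2 | 4.6% | 4.9% | 90.1% | 91.0% | 0.9 |
| 3 / 3 | 4.1% | 5.0% | 90.8% | 92.7% | 1.9 |
| 5 / 3 | 3.6% | 5.0% | 91.5% | 94.2% | 2.7 |

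Over other stratum shares, and a null rate of 42.5% as well as 30%, Pearson's type I error was 4.2-4.7% at odds ratio 2 for each factor and 2.9-3.9% at 5 and 3. Block sizes 2, 4, 6 and 8 gave the same picture. With dose as the only stratum (odds ratio 2), type I error was 4.8-4.9% and the gain 0.4-0.6 points.

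**4. A second set of assumptions.** Strata of 65/16/65/16, placebo rates for lower/higher dose:

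- Moderate: US 22/18%, non-US 40/35%. Type I error is 4.7% for Pearson and 5.0% for CMH. With the overall rates set to 30% and 55%, power is 90.4% against 91.3%.
- Strong: US 15/10%, non-US 45/40%. Type I error is 3.8% against 5.0%; power, set the same way, is 91.6% against 93.9%.

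**5. ANCOVA.** Assumed standardised effect 0.5, 160 subjects, 8,000 null trials and 4,000 trials for power. If the strata explain 5, 10 or 20% of the variance left after baseline, type I error without strata is 4.5, 4.1 and 3.2%, against 5.0-5.3% with strata. Power lost is about 1.4, 2.1 and 3.6 points.

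**The case against.** The best defence is that the planned primary test is valid. Its type I error stays at or below about 5%, so a significant Pearson result stands. At the plan's own rates it delivers the promised 90%. The harm depends wholly on stratum effects that the documents do not report. All of this stands, and it is why the point is graded as an improvement.

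Three stronger readings are tempting and not supported.

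- *That the mismatch distorts error rates in a harmful direction.* It does not: the error is conservative only.
- *That ignoring the strata could drop power well below 90%.* In the strong pattern of step 4, applying a fixed odds ratio of 2.85 within each stratum gives Pearson about 81% and CMH about 85%. But those inputs shrink the overall rates to 29.0% against 50.4%: placebo (65 × 0.15 + 16 × 0.10 + 65 × 0.45 + 16 × 0.40)/162 = 47/162 = 29.0%. With the same overall rates and no stratum effect, Pearson has 79.5%. The fall from 90% comes from a smaller treatment effect, not from the choice of test. That pattern also assumes a location odds ratio of about 4.6, since (0.45/0.55)/(0.15/0.85) = 4.6, for which the documents offer no basis.
- *That the strata are ignored everywhere.* Text after the efficacy paragraph is redacted, missing-data detail is deferred to a statistical analysis plan, and the mixed model lists no terms. A supplementary adjusted analysis cannot be excluded. This does not change the primary test, which is fully readable and unstratified.

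The difference between Sections 12.1 and 16.1.1 is a separate documentary matter. Section 12.1 omits location and does not deny it, so it adds no weight to the statistical point.

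**Conclusion.** The mismatch is real and its consequence is small. If location or prednisone dose predicts SRI response, the primary test is conservative, with type I error of about 3.8-4.7% in the strong and moderate patterns of step 4 and lower only at the most extreme effects tried. At 30% against 55%, a stratified test would add about 1 point of power for moderate stratum effects and 2-3 points for strong ones, to Pearson's 90-91%. If the strata do not predict response, the two tests perform alike. The stated power and sample size are correct.

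The direction follows from the design. The sizes rest on assumed stratum shares and effects, a common treatment odds ratio, and nearly complete balance within strata. This is a free improvement, not a must-fix.

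**What to change.** - In Section 21.6, make the primary test a two-sided CMH test at 0.05, stratified by location and prednisone-equivalent dose as randomised. Report the Mantel-Haenszel risk difference with its 95% CI. Keep the unstratified Pearson test as a sensitivity analysis, and say what the small-count fallback becomes under stratification.
- Use CMH for the secondary proportions.
- Add both factors to the ANCOVA, and to any mixed model, whose terms should be listed.
- Reconcile Section 12.1 with Section 16.1.1 so that both name the factors actually used.

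The cost is wording in the protocol and SAP, settled before unblinding. It needs no new data, visits or subjects, and power is essentially unchanged if the strata turn out not to matter.
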